## **10.3 Efficacy Analysis**

The accepted PP population used for BE evaluation includes all randomized subjects who meet all inclusion/exclusion criteria, instill a pre-specified proportion of the scheduled doses (i.e., compliance between 75 to 125%) of the assigned product for the specified duration of the study,

and complete evaluations at Day 14 (Week 2) and Day 42 (Week 6) with no protocol violations that would affect the treatment evaluation.

Subjects whose condition worsens (e.g., IOP  $\geq$  36 mm Hg in either eye) and require alternate or supplemental therapy for the treatment of their chronic open angle glaucoma or ocular hypertension during the study should be discontinued, excluded from the PP population analysis, and provided with effective treatment.

Analysis will be done in both eyes. The primary analyses will be completed by constructing two-sided 95% confidence intervals of the treatment difference (test – reference) for mean IOP of both eyes (continuous variable) at all four follow-up points (i.e., at approximately 8:00 a.m. [hour 0; before the morning drop] and 10:00 a.m. [hour 2] at the Day 14 [Week 2] and Day 42 [Week 6]) visits. This mean IOP must be within  $\pm$  1.5 mm Hg using the PP population for all time points measured and within  $\pm$  1.0 mm Hg using the PP population for the majority of time points measured. Additional details of the statistical approach considering country wise analysis will be provided in the SAP.

For change from baseline IOP, baseline will refer to the time-matched measure at Visit 2. For all other variables, baseline is defined as the last measurement prior to the first dose of study medication. Change from baseline will be calculated as visit – baseline. The p-values for testing equivalence of these time-matched means between treatment groups will be generated using the TOST (two one-sided tests) procedure at each of the equivalence limits (-1.0, 1.0) and (-1.5, 1.5).

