8.6 Sample Size Calculation

An equivalence test of means using two one-sided tests on data from a parallel-group design with sample sizes of 266 in the SPIL's Brinzolamide ophthalmic suspension 1% and 266 in Azopt® 1% achieves 90% power at an $\alpha = 0.05$ significance level when the true difference between the means is 0, the standard deviation is 3.5, and the 95% equivalence limits are -1.0 and 1.0.

Considering the possibility of 20% of subjects not being evaluable either due to dropping out of the study or having major protocol violations, approximately 333 subjects will be enrolled in each treatment group for a total of 666 subjects in the study.

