9.6.1 Primary Efficacy Endpoint

Mean difference in IOP of both eyes between the two treatment groups at four time points, i.e., at approximately 8:00 a m. (hour 0; before the morning drop) and 10:00 a.m. (2 hours) at the Day 14 (Week 2) and Day 42 (Week 6) visits

IOP measurements will be taken using a Goldmann applanation tonometer. IOP will be measured at least twice in each eye with the right eye measured first. If the difference of the first 2 measurements is ≤ 1 mm Hg, the average of these 2 measurements will be used as the IOP data for this eye. If the difference is > 1 mm Hg, a third measurement will be taken, and the median of these 3 measurements will be used as the IOP data for this eye.

Two-sample 95% CIs around the difference in the mean IOP (both eyes) at each timepoints i.e., at approximately 8:00 a m. [hour 0; before the morning drop] and 10:00 a.m. [hour 2] at the Day 14 [Week 2] and Day 42 [Week 6]) visits will be constructed using a two-sample t-distribution.

The hypotheses for a two-sample equivalence test are:

 H_o : $\mu < \Theta_L$ or $\mu > \Theta_U$

[figure not shown]
 $H_1: \Theta_L \le \mu \ge \Theta_U$

Where.

μ: Difference in mean IOP between treatment groups within study period

 $\Theta_{L:}$ -1.5mm Hg and (-1.0mm Hg)

 $\Theta_{U:}$ 1.5mm Hg and (1.0mm Hg)

The overall p-value of the equivalence test will be reported, which is the larger of the two p-values of the tests L and U. Rejection of H_0 in favour of H_1 at significance level α occurs if and only if the 100 (1-2 α) % confidence interval for μ is contained within (-1.5, 1.5) and (-1.0, 1.0). Two sample t-test also assumes equality of variances in the treatment groups, hence depending on the results from Levene's test, CI, and p-values from Equal (Pooled) or Unequal (Satterthwaite) variance will be reported.

This analysis also will be tested for ITT population to check the robustness of the result.

[figure not shown]

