9.7 Data Manipulation and Subgroup Analyses

Not Applicable.

10 Deviation from the Study Protocol

Not Applicable.

11 Database Lock and Unblinding

The SAP will be finalized prior to database lock. After the data cleaning process is finalized according to the data management plan (DMP) and the assignment of patients to the analysis sets is agreed and signed by the sponsor, the study database will be locked.

12 References

Not Applicable

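### SAP 9.6.1 does not state the protocol's primary success rule: α has no value, two nested margins are joined by 'and', and nothing combines the four time points

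*SAP*

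**What the plan says.** **Protocol 10.3** (and the synopsis) sets one rule for the per protocol (PP) population. "The primary analyses will be completed by constructing two-sided 95% confidence intervals of the treatment difference" at four time points: hours 0 and 2 at Weeks 2 and 6. The result must be within ±1.5 mm Hg at every time point and within ±1.0 mm Hg "using the PP population for the majority of time points measured". The same section adds p-values from the two one-sided tests "procedure at each of the equivalence limits (-1.0, 1.0) and (-1.5, 1.5".

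**SAP 9.6.1** starts with "Two-sample 95% CIs around the difference in the mean IOP (both eyes) at each timepoints". It then defines a single parameter μ as "Difference in mean IOP between treatment groups within study period" and rejects the null if and only if the 100(1−2α)% interval for μ "is contained within (-1.5, 1.5) and (-1.0, 1.0". The section gives no number for α and no rule for combining the four results.

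**SAP 9.6.2** does contain the all/majority sentence, but under the secondary endpoint, change from baseline.

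**SAP 8.6** and **protocol 10.5** give the only numeric α, 0.05, for 266 evaluable subjects per arm and 90% power, where "the standard deviation is 3.5, and the 95% equivalence limits are -1.0 and 1.0".

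Under the SAP heading "10 Deviation from the Study Protocol" the entry is that none applies.

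**The concern.** This is the sole decision rule of an equivalence trial, and SAP 9.6.1 departs from the protocol in three ways.

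1. **Margins.** An interval inside ±1.0 is always inside ±1.5, so the literal 'and' removes the ±1.5 margin. If 'and' merely lists two separate tests, the section has no success rule.
2. **Time points.** One μ for the study period is not four differences, and nothing says how many of the four must pass.
3. **Level.** A 95% interval corresponds to α = 0.025 in the 100(1−2α)% formula. The only α in the documents, 0.05, gives a 90% interval.

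The SAP declares no deviation from the protocol, and neither document says which text prevails. The same data could then be called equivalent under one text and not under the other, and the choice could be made after unblinding.

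**Working it through.** **Inputs.** From SAP 8.6 and protocol 10.5: SD 3.5 mm Hg, 266 evaluable per arm, true difference 0, margin ±1.0, α 0.05, power 90%, 20% not evaluable. From protocol 10.3: 95% intervals, ±1.5 at all time points, ±1.0 at the majority (at least 3 of 4). Assumed, because the documents do not say: equal correlation between time points, from 0 to 0.9, and SAP 9.6.1 applied at every time point.

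**1. The plan's own figure.** SE = 3.5 × √(2/266) = 0.3035. Normal approximation to power at one time point: 2Φ(1.0/SE − z) − 1, with 1.0/SE = 3.295.

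- α = 0.05 per one-sided test: 2Φ(3.295 − 1.645) − 1 = 0.901. The t version, integrating over the variance estimate, gives 0.9002. The stated 90% is reproduced, and 266/0.8 = 332.5, rounded up to 333 per arm.
- α = 0.025 (the 95% interval): 2Φ(3.295 − 1.960) − 1 = 0.818; t version 0.8162. The stated 90% is not reproduced.

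**2. What each rule requires.** Half-widths on 530 df are 0.500 (90% interval) and 0.596 (95% interval).

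- Protocol: every estimate within 1.5 − 0.596 = 0.904 of zero, and at least three within 1.0 − 0.596 = 0.404.
- Literal SAP with α = 0.05: all four within 1.0 − 0.500 = 0.500.

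Two illustrations show conflict in each direction:

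- Estimates 0.1, 0.2, 0.3, 0.7 pass the protocol rule and fail the literal SAP rule (0.7 > 0.500).
- Estimates 0.1, 0.1, 0.45, 0.45 pass the literal SAP rule and fail the protocol rule (only two within 0.404).

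**3. How often this happens.** Four equicorrelated normal differences, half-widths held at the values above, 1,000,000 replicates per setting, true difference 0:

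| Correlation | 0 | 0.3 | 0.5 | 0.7 | 0.9 |
|---|---|---|---|---|---|
| Protocol rule, 95% intervals: pass | 0.838 | 0.830 | 0.818 | 0.806 | 0.799 |
| Literal SAP, 90% intervals: pass | 0.657 | 0.680 | 0.713 | 0.761 | 0.825 |
| The two disagree | 0.241 | 0.209 | 0.163 | 0.108 | 0.061 |
| Only the protocol rule passes | 0.211 | 0.179 | 0.134 | 0.077 | 0.018 |
| Only the SAP rule passes | 0.030 | 0.029 | 0.029 | 0.032 | 0.043 |
| Literal SAP, α = 0.025: pass | 0.445 | 0.475 | 0.523 | 0.597 | 0.697 |

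At a true difference of 0.5 the protocol rule passes 0.132 to 0.334, the literal SAP rule (90% intervals) passes 0.062 to 0.368, and they disagree in 0.069 to 0.120.

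**4. The reading kindest to the SAP.** Import the all/majority rule into 9.6.1 and leave only α open. With 90% intervals it passes about 89% to 95% of trials; with 95% intervals, 80% to 84%. The first rule contains the second, so the verdict changes in the difference: about 9% (correlation 0.9) to 11% (correlation 0). At a true difference of 0.5 it changes in about 13% to 16%.

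**The case against.** The protocol rule is clear and appears twice. The SAP repeats it in 9.6.2 in wording that fits the primary endpoint better than change from baseline, so it may simply sit under the wrong heading. Together with the declaration of no deviation, this suggests that the sponsor means the protocol rule. The 'and' more naturally lists two tests, as protocol 10.3 does. If 95% intervals and the all/majority rule are also read in, the conflict disappears. No passage names a 90% interval for the primary analysis. With 95% intervals the literal SAP rule is strictly tighter than the protocol rule, so every conflict would be a missed claim of equivalence, not a false one. Zero correlation between repeated readings in the same subjects is implausible.

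Much of this stands. The absence of a combining rule is a fault of 9.6.1, not of the whole SAP. α is better described as caught between two implied values than as absent from the documents. A verdict favouring only the SAP rule requires the 90% reading, and the 24% figure is the extreme of the range. False claims are not the main risk: at a true difference of 1.0 the literal SAP rule with 90% intervals passes only about 2% of trials at most.

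It does not remove the problem. Each benign reading has to be supplied by the reader. Even the kindest leaves α open, at a cost of 9% to 11% of verdicts. If α is 0.025 and the 'and' is literal, disagreement grows: 0.838 − 0.445 = 39% at correlation 0 and 0.799 − 0.697 = 10% at 0.9.

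**Conclusion.** The concern holds. SAP 9.6.1 does not fix the primary decision rule and does not match protocol 10.3. At the design values and a true difference of 0, the protocol rule and the literal SAP rule with α = 0.05 disagree in 6% to 24% of trials, mostly but not only by the SAP rule failing trials that the protocol rule passes; at correlation 0.9 the balance reverses. These rates depend on the assumed correlation and on applying 9.6.1 at every time point. The textual mismatch depends on neither.

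The stated 90% power belongs to a 90% interval. With the 95% interval that both documents name, power at one time point is about 82%. This must be corrected before the analysis, because it concerns whether the products are declared equivalent.

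**What to change.** Replace the rejection sentence in SAP 9.6.1 with:

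> Equivalence is concluded in the PP population if and only if the two-sided 95% CIs for test minus reference lie within (−1.5, 1.5) mm Hg at all four time points and within (−1.0, 1.0) mm Hg at three or more of the four.

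In the same section, state α = 0.025 per one-sided test, compare the p-values from the two one-sided tests with 0.025, and define μ separately for each time point. In SAP 9.6.2, label the all/majority rule as supportive.

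In SAP 8.6, protocol 10.5 and the synopsis, restate power at one time point as about 82% for 266 per arm and ±1.0. For information only: 90% at that level would take 320 evaluable per arm, or 320/0.8 = 400 randomized per arm. The wording fix does not depend on enlarging the trial.

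The cost is a few sentences and a restated power figure, with no new data. Make the change before database lock and unblinding. The documents do not show whether lock has occurred; if it has, record the change as a dated post-lock clarification.

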## **10.5 Sample Size**

An equivalence test of means using two one-sided tests on data from a parallel-group design with sample sizes of 266 in the SPIL's Brinzolamide ophthalmic suspension 1% and 266 in Azopt® 1% achieves 90% power at an  $\alpha = 0.05$  significance level when the true difference between the means is 0, the standard deviation is 3.5, and the 95% equivalence limits are -1.0 and 1.0.

Considering the possibility of 20% of subjects not being evaluable either due to dropping out of the study or having major protocol violations, approximately 333 subjects will be enrolled in each treatment group for a total of 666 subjects in the study.

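### SAP 9.6.1 states the primary equivalence rule in a form that reduces to ±1.0 mm Hg alone and gives no rule across the four time points; the protocol's rule (±1.5 at all, ±1.0 at a majority) is missing there

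*SAP*

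**What the plan says.** **SAP 9.6.1 (primary endpoint).** A two-sample 95% confidence interval is built at each of the four time points (hours 0 and 2 at Weeks 2 and 6). One pair of hypotheses follows, with two sets of limits, ±1.5 and ±1.0 mm Hg. The null is rejected if and only if the 100(1−2α)% interval "is contained within (-1.5, 1.5) and (-1.0, 1.0"). One overall p-value is reported, the larger of the two one-sided values. The parameter μ is defined as "Difference in mean IOP between treatment groups within study period", with no index for time point. The alternative is printed as "H_1: \Theta_L \le \mu \ge \Theta_U". Nothing in 9.6.1 says at how many time points either limit must be met.

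**Protocol synopsis and 10.3.** Two-sided 95% intervals for test minus reference are built at all four time points. The next sentence begins "This mean IOP must be within", sets ±1.5 for all time points, and then ±1.0 "mm Hg using the PP population for the majority of time points measured". Section 10.3 also asks for TOST p-values at each pair of limits separately.

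**SAP 9.6.2 (secondary endpoint, change from baseline).** This section holds both the rejection sentence of 9.6.1 and the protocol's all/majority sentence. It is the only place in the SAP where the majority rule appears.

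**SAP Section 10** reports no deviation from the protocol.

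**The concern.** This is the trial's pass/fail rule, and the section that the primary analysis will be programmed from does not contain the protocol's version of it. Taken literally, 9.6.1 makes the ±1.5 limit redundant and leaves the combination of time points to the reader. A programmer could require ±1.0 at every time point, or could bring the majority rule over from 9.6.2 or from the protocol. These choices can give opposite verdicts on the same data. If the results fall between them, the choice would be made after the results are known. A single p-value also cannot serve two different margins.

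**Working it through.** **Reproducing the plan's figure.** Inputs from Protocol 10.5 and SAP 8.6: α = 0.05 for each one-sided test, 90% power, margin ±1.0, and "when the true difference between the means is 0, the standard deviation is 3.5".
- n per arm = 2 × [3.5 × (1.645 + 1.645) / 1.0]² = 265.1, rounded up to 266.
- Allowing for 20% not evaluable: 266 / 0.8 = 332.5, rounded up to 333 per arm.

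The stated sizes reproduce, for one comparison at ±1.0 with a 90% interval.

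**Interval half-width at 266 per arm.**
- SE = 3.5 × √(2/266) = 0.3035.
- 95%: 1.964 × 0.3035 = 0.596. A time point meets ±1.0 if the observed difference is below 1.0 − 0.596 = 0.404 in absolute value, and ±1.5 if it is below 1.5 − 0.596 = 0.904.
- 90%: 1.648 × 0.3035 = 0.500, so the cut-offs are 0.500 and 1.000.

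**One data set, two verdicts.** Take observed differences of 0.1, 0.1, 0.1 and 0.6.
- 95% intervals: (−0.50, 0.70) three times and (0.00, 1.20) once.
- 90% intervals: (−0.40, 0.60) three times and (0.10, 1.10) once.

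At either level all four lie inside ±1.5 and three of four inside ±1.0, so the protocol rule applied to intervals is met. The fourth time point is not inside ±1.0, so a rule of ±1.0 at every time point fails.

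**How often this happens.** The correlation between time points is not in the documents. I assume it is equal for all pairs and between 0.5 and 0.9. The four estimated differences are treated as jointly normal with mean 0 and SE 0.3035, and the half-width as fixed. Given the shared component u, let p(u) be the chance that one time point meets ±1.0 and q(u) the chance that it meets ±1.5. Averaging over u:
- ±1.0 at all four: E[p⁴].
- Protocol rule on intervals: E[p⁴ + 4p³(q − p)].
- Meets the protocol rule but not ±1.0 at all four: E[4p³(q − p)].

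| Interval | Correlation | ±1.0 at all four | Protocol rule on intervals | Disagree |
|---|---|---|---|---|
| 95% | 0.5 | 52.4% | 81.9% | 29.5% |
| 95% | 0.7 | 59.6% | 80.6% | 20.9% |
| 95% | 0.9 | 69.8% | 79.9% | 10.1% |
| 90% | 0.5 | 71.4% | 91.7% | 20.3% |
| 90% | 0.7 | 76.0% | 90.1% | 14.1% |
| 90% | 0.9 | 82.5% | 89.2% | 6.7% |

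Disagreement runs one way only, because any trial that meets ±1.0 at all four also meets the protocol rule.

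**The case against.** The strongest reply is that 9.6.1 describes a test for one μ and lists two sets of limits, so its conjunction may simply name two tests, as Protocol 10.3 does. The SAP places the same sentence beside the majority rule in 9.6.2, which suggests that its authors saw the two as compatible. Section 10 claims no departure from the protocol. This has force. A reader might infer that the SAP deliberately replaced the majority rule with ±1.0 at all four time points, and the documents do not support that: 9.6.1 never says all four must pass. What remains is that on either reading 9.6.1 has no combining rule, and that its if-and-only-if sentence is wrong as a statement of the protocol's criterion.

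Two other inferences should be resisted.
- The protocol sentence that opens "This mean IOP must be within" might be read as a criterion on the point estimate. Observed differences of 0.8 at all four time points would then pass, although the 95% intervals of (0.20, 1.40) do not meet ±1.0. But the sentence directly follows the one that constructs the intervals, and both the TOST wording and the sample-size basis point to intervals. It is loose drafting, not a further competing rule.
- The printed alternative might suggest that the reported p-value supports non-equivalence. Only the second inequality sign is reversed. The null is oriented correctly, and both the containment rule and the p-value are defined operationally, so no computed result changes. The sign may even come from reading the PDF. Whether the limit itself counts as equivalent makes no practical difference for a continuous estimate.

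The size also depends on the interval level, which is why both levels are tabulated.

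**Conclusion.** The concern holds as a defect in the stated decision rule of the primary-endpoint section. Literally, 9.6.1 reduces to ±1.0 alone and is silent on the four time points, while the protocol asks for ±1.5 at all and ±1.0 at a majority. If the silence is filled with ±1.0 at all four, the probability of passing at a true difference of 0 falls from 80%–82% to 52%–70% with 95% intervals, and from 89%–92% to 71%–82% with 90% intervals. The verdicts differ in 10% to 29.5% and 7% to 20% of trials respectively.

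These figures rest on 266 evaluable subjects per arm, SD 3.5, and the assumed equal correlation of 0.5 to 0.9. A lower correlation widens the gap. They measure what is at stake in the unclear wording; they do not show that the sponsor intends the stricter rule. The correction should be made before the SAP is finalized, because it settles the pass/fail criterion and needs only wording.

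**What to change.** In SAP 9.6.1:
- For each time point k = 1 to 4, define δ_k as mean IOP on test minus mean IOP on reference.
- For D = 1.5 and D = 1.0 separately, state H0: δ_k ≤ −D or δ_k ≥ D, against H1: −D < δ_k < D. This also corrects the printed alternative.
- Conclude equivalence if and only if, in the PP population, the confidence interval for δ_k lies within (−1.5, 1.5) at all four time points and within (−1.0, 1.0) at three or more.
- Report a TOST p-value for each limit at each time point, as Protocol 10.3 already requires, in place of one overall p-value.

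Remove the joint reference to the ±1.0 limits from the rejection sentence in both 9.6.1 and 9.6.2. In the protocol synopsis, Protocol 10.3 and SAP 9.6.2, make the confidence interval for the mean difference the subject of the all/majority sentence.

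Name one interval level and use it in both documents. Both now construct two-sided 95% intervals, while the SAP's 100(1−2α)% at α = 0.05 is 90%. Without a named level the corrected rule would still be open.

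The cost is a SAP revision and a matching protocol clarification. SAP Section 11 already places finalization before database lock. No new data, subjects or additional analyses are needed.

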9.6.2 Secondary Efficacy Endpoints

Change from baseline in IOP of both eyes between the 2 treatment groups at 4 time points, i.e., at approximately 8:00 AM. (hour 0; before the morning drop) and 10:00 AM. (hour 2) at the Day 14 (Week 2) and Day 42 (Week 6) visits.

For change from baseline IOP, baseline will refer to the time-matched measure at Visit 2. Change from baseline will be calculated as visit x – baseline. The overall p-value of the equivalence test will be reported, which is the larger of the two p-values of the tests L and U. Rejection of H0 in favour of H1 at significance level α occurs if and only if the 100 (1-2 α) % confidence interval for μ is contained within (-1.5, 1.5) and (-1.0, 1.0). Two sample t-test also assumes equality of variances in the treatment groups, hence depending on the results from Levene's test, CI and p-values from Equal (Pooled) or Unequal (Satterthwaite) variance will be reported. This mean IOP must be within \pm 1.5 mm Hg using the PP population for all time points measured and within \pm 1.0 mm Hg using the PP population for the majority of time points measured.

This analysis also will be tested for ITT population to check the robustness of the result.

In addition to these individual confidence intervals, a mixed effects repeated measures model, with random effect for subject, covariate for baseline IOP, and fixed effects for treatment and day/time (within subject repeated measures) will be fitted to the data. Appropriate covariance structure will be used to model the within subject, between time point variances with order of treatment Visit treatment*visit and baseline as covariate. Individual and simultaneous confidence intervals will then be constructed based on this MMRM model at each of the time points. The 95% simultaneous confidence intervals will use the Tukey-Kramer method to adjust for multiple comparisons across all 4 time points. Above mentioned analysis will be performed on PP and ITT population.

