## **11.7 Amendments to the Protocol**

All changes or deviations of the trial must be confirmed in writing. The amendments to protocol will be made jointly between the CRO (if applicable), the Sponsor and Investigator(s). Protocol amendment(s) will be signed off in the same way as the protocol.

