8.2 Analysis Population

Analysis Population	Definition
All Screened Population	All patients who have signed the informed consent form
Intent-to-Treat Population	The Intent-to-Treat (ITT) population consists of all subjects who are randomized into the study. and ITT based analysis will be used as confirmatory analyses
Per Protocol Population	The PP population includes all randomized subjects who meet all inclusion/exclusion criteria, and complete evaluations at week 2, week 6 (with compliance between 75 to 125%) with no major protocol deviations that would affect the treatment evaluation (primary endpoint). The PP population will be considered the primary analysis population for the study and will summarize subjects as treated.
Safety Population	The safety population includes all subjects who receive at least 1 dose of study medication. The safety population will be used to summarize safety variables and will summarize subjects as treated.

Note: As there are multiple examples of violations to GCP and ALCOA principles, all the data reported from Site # 122 is not reliable. Hence, based on the clinical investigation report dated 13 Sep 2023, it has been agreed to remove all the 20-subject data from the efficacy analysis These 20 subjects will be included in the safety analysis of the study data. However, safety data will be presented with and without subjects from Site #122.

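### Tukey-Kramer does not fit the four test-minus-reference differences: the supportive 95% simultaneous intervals come out 3% or 21% wider than Bonferroni, depending on a family the plan does not state

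*SAP*

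**What the plan says.** SAP 9.6.2 adds a model to the t-based equivalence intervals: "In addition to these individual confidence intervals, a mixed effects repeated measures model", with subject as random effect, baseline IOP as covariate, and terms for treatment, time and their interaction. From this model, "Individual and simultaneous confidence intervals will then be constructed based on this MMRM model at each of the time points". The adjustment is then named: "The 95% simultaneous confidence intervals will use the Tukey-Kramer method to adjust for multiple comparisons across all 4 time points". The analysis is to be run on both PP and ITT.

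Protocol 10.3 carries the same adjustment sentence. Its fixed effects are treatment and day/time. Only the SAP adds an interaction, written as treatment by visit.

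The intervals that decide equivalence are separate. SAP 9.6.1 plans "Two-sample 95% CIs around the difference in the mean IOP (both eyes) at each timepoints", with no multiplicity adjustment. In protocol 10.3 and SAP 9.6.1 to 9.6.2, the limits of ±1.5 mm Hg (all time points) and ±1.0 mm Hg (the majority) belong to those individual intervals.

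**The concern.** Tukey-Kramer gives joint coverage for all pairwise differences among one set of *k* means. The endpoint here is a between-group difference at four time points, so the family of interest is four contrasts, one per time point. That is not an all-pairs family:

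- **8 treatment-by-time means:** 8 × 7 / 2 = 28 pairs are protected and 4 are wanted. The other 24, such as test at Week 2 against reference at Week 6, answer no question in this trial.
- **4 time-point means:** 4 × 3 / 2 = 6 pairs are protected, and none is a treatment difference.
- **4 treatment-by-visit means** (if visit in the SAP interaction means only Week 2 and Week 6): two of the 6 pairs are treatment differences, but per visit, not at each of the four time points.

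The plan does not say which set is meant, so the interval width cannot be reproduced from the text. At stake is how the supportive PP and ITT results read. In an equivalence trial, needless width makes the product look less well characterised than the data allow.

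**Working it through.** **Inputs from the documents.** SD 3.5 mm Hg, 266 evaluable per arm, limits ±1.0, true difference 0, α = 0.05 (protocol 10.5, SAP 8.6); 666 randomised 1:1 (SAP 7.1.2); two groups and four time points (SAP 9.6.2). For ITT, the SAP 8.2 note on Site 122 states that "it has been agreed to remove all the 20-subject data from the efficacy analysis", leaving 666 − 20 = 646, or about 323 per arm if the removal is balanced (an assumption).

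**The plan's own figure.** The documents give no multiplier or width for the simultaneous intervals, so the stated power serves as the check on the inputs.

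- SE = 3.5 × √(2/266) = 0.3035.
- TOST power at one-sided 0.05 per test = 2Φ(1/0.3035 − 1.645) − 1 = 0.901 (0.900 with the t distribution). The stated 90% reproduces.

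**Multipliers** (df = 2 × 266 − 2 = 530). Tukey-Kramer is the 95% studentized-range quantile for *k* means divided by √2. Bonferroni for four contrasts is t(1 − 0.05/8).

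| Method | Multiplier | Ratio to Bonferroni |
|---|---|---|
| Tukey-Kramer, k = 8 | 3.043 | 1.214 |
| Tukey-Kramer, k = 4 | 2.577 | 1.028 |
| Bonferroni, 4 contrasts | 2.506 | 1 |
| Unadjusted (same as Tukey with k = 2) | 1.964 | 0.784 |

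For df from 100 to 100,000 the excess over Bonferroni is 21.3–21.7% (k = 8) and 2.7–2.9% (k = 4). These ratios do not depend on SD or on the correlation between time points.

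**Sample-size equivalent.** Width scales with 1/√n. Squared ratios: 1.214² = 1.474 and 1.028² = 1.057. The k = 8 interval is as wide as a Bonferroni interval from 266/1.474 = 180 per arm (32% fewer); for k = 4 it is 266/1.057 = 252 per arm (about 5% fewer).

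**Against an exact joint adjustment.** The 95% quantile of the largest |t| among four equally correlated contrasts was simulated. The correlation is not in the documents and is assumed to run from 0 to 0.9.

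| Assumed correlation | Exact multiplier | Excess, k = 8 | Excess, k = 4 |
|---|---|---|---|
| 0 | 2.498 | 22% | 3% |
| 0.5 | 2.449 | 24% | 5% |
| 0.9 | 2.242 | 36% | 15% |

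The lowest joint coverage, at correlation 0, is 99.0% for k = 8 and 96.0% for k = 4. Both exceed 95%.

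**Half-widths in mm Hg** (multiplier × SE, SD 3.5). An assumed baseline correlation of 0.5 multiplies the SE by √(1 − 0.25).

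| Set | SE | k = 8 | k = 4 | Bonferroni |
|---|---|---|---|---|
| PP, 266 per arm, no baseline gain | 0.3035 | 0.92 | 0.78 | 0.76 |
| PP, baseline correlation 0.5 | 0.2628 | 0.80 | 0.68 | 0.66 |
| ITT, 323 per arm, no baseline gain | 0.2754 | 0.84 | 0.71 | 0.69 |
| ITT, baseline correlation 0.5 | 0.2385 | 0.73 | 0.61 | 0.60 |

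Missing data would widen every entry; the ratios would hold.

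**Illustration.** With true difference 0, SD 3.5 and 266 per arm, the chance that one simultaneous interval lies within ±1.0 is 2Φ(1/SE − multiplier) − 1: 57% for Bonferroni, 53% for k = 4 and 20% for k = 8.

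**A programming risk.** Running Tukey separately within each time point means k = 2 and multiplier 1.964, which is no adjustment. Joint coverage would be about 82% to 91% over correlations 0 to 0.9. That contradicts an adjustment across all four time points, but clearer wording would rule it out.

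**The case against.** The strongest reply is that nothing turns on this. The intervals are supplementary, conservative and used by no success rule, so preferring a sharper valid method over a wider one is partly taste. That stands as far as severity goes: the point is minor.

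A second reply is that 21% needs k = 8, which the plan never states. On the more literal reading, k = 4, the loss is 2.8%, or 0.02 mm Hg (0.782 against 0.761). This is also fair, and is why both figures are given. It does not rescue the method: under k = 4 the protected pairs are still not the four treatment differences, and the reader cannot tell which width will be reported.

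Third, the protocol's model lists no treatment-by-time interaction and, taken as written, gives one common difference rather than four. But the protocol also asks for intervals at each time point, and the SAP supplies the interaction. A four-level treatment-by-time term settles this and the treatment-by-visit reading together.

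Last, protocol and SAP now agree on this sentence, and changing it late creates a departure from the protocol. That cost is real but small: the change touches no decision rule and can be documented openly before lock.

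**Conclusion.** The plan names a method built for a different family of comparisons. Under either reading that adjusts across the four time points, the supportive simultaneous intervals are valid but too wide: by 2.8% (4 means) or 21.4% (8 means) against Bonferroni. Against an exact joint adjustment the excess is 3–15% or 22–36% over assumed correlations of 0 to 0.9. The Bonferroni comparison rests only on the number of means; the half-widths in mm Hg also rest on SD 3.5, the sample sizes and the assumed baseline gain. The primary equivalence conclusion is not affected. Severity is minor, confidence high.

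**What to change.** In SAP 9.6.2:

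1. State the family, for example: *The family is the four test-minus-reference differences, one per time point, from a treatment-by-time-point term with four levels (Week 2 and Week 6, each at 8:00 and 10:00).*
2. Replace Tukey-Kramer with a multivariate-t (simulation-based) adjustment over these four contrasts, which uses the estimated correlation between time points. The simple alternative is Bonferroni: four 98.75% intervals, multiplier 2.51.
3. Record the change under "10 Deviation from the Study Protocol", which now reads Not Applicable. The SAP sets the timing: "The SAP will be finalized prior to database lock".

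Protocol 10.3 can be aligned at the next amendment; under protocol 11.7, "Protocol amendment(s) will be signed off in the same way as the protocol".

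The cost is two sentences in the SAP, one entry in its section 10 and a small code change. No new data, visits or subjects are needed.
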